Multicenter validation of the Scandinavian Guidelines for management of minimal, mild and moderate head injury in adults: a study protocol.

Principal investigator:

[name], PhD
Pediatric department, Halland Hospital Halmstad

Date of protocol: 30th of august 2017

Multicenter validation of the Scandinavian Guidelines for management of minimal, mild and moderate head injury in adults: a study protocol.

Introduction

Traumatic brain injuries (TBI) are one of the most common reasons for patients to attend the emergency department (ED) with an estimated incidence in Europe of 260 per 100 000 for admitted TBI^{1, 2, 3}. Approximately 90% of patients with TBI are defined as mild TBI (mTBI)⁴. These patients have a normal or minimally altered level of consciousness and Glasgow Coma Scale (GCS) 13 to 15 when attending the ED.

A small minority of patients with mTBI would show pathological results, such as intracranial hemorrhages or cerebral contusions on a computed tomography (CT), and even fewer need neurosurgical intervention⁵. Nevertheless, complications would be so severe, if neurosurgical intervention is delayed, that it has become common practice to subject all patients with mTBI to CT⁶. The high number of CT scans has an impact on health care resources but may also involve risk by subjecting patients through potentially harmful ionizing radiations⁷.

In the past years, several independent research groups have attempted to optimize CT use in mTBI patients by forming guidelines that aim to identify patients at high risk for intracranial complications⁸. Most guidelines have been published in the past 15 years and have been validated both prospectively internally and externally; all guidelines have been shown to be safe when implemented in clinical use with few missed complications. However the number of CT scans has not been reduced dramatically, in some cases it has even increased⁹.

In 2013, the new Scandinavian guidelines (SNC13) were published. They are the first guidelines that use a biomarker, S100B, as a tool for managing patients with mTBI. Although S100B has a low specificity for intracranial complications, a high sensitivity makes it suitable to be implemented into clinical practice as a tool for CT reduction.

Previous SNC guidelines have been compared to other prominent guidelines with impressive results¹⁰. The SNC13 have been externally validated in a retrospective multicenter center study from the USA that was underpowered for important outcomes¹¹. Nevertheless, SNC13 have already been partially implemented in clinical practice in Scandinavia. However, a strict

multicenter validation has not been performed yet nor a systematic comparison to other available guidelines.

Aims

Our primary aim is to validate the performance of the SNC13 in predicting intracranial complications in adult patients presenting with traumatic head injury in Swedish hospitals. A secondary aim is to compare the performance of SNC 13 with 6 other clinical guidelines, with respect to important outcomes. Moreover, we want to explore the performances of different biomarkers in predicting intracranial complications in predefined subgroups of TBI. Finally, we want to evaluate the possibility of further improvement of the SNC13 guidelines.

Methods

Design

We will perform a prospective, multicenter, pragmatic, observational study of adults presenting with traumatic head injury at the ED.

All data necessary for analysis including predictor variables and outcome data for all the seven guidelines included in the study will be registered (table 1). Patients will be managed clinically accordingly to the judgment of the responsible physician and/or local guidelines.

Study setting and population

The study will be set in Halmstad, Malmö, Lund, Örebro and Linköping, Sweden. Hallands Hospital Halmstad (HS) is a level II trauma centre, Skåne University Hospital in Malmö and Lund (SUS), Örebro University Hospital, Linköping University Hospital are level I trauma centers.

The coordinating site for the study will be HS where the statistical and the comparative biomarker analysis will be performed.

Inclusion criteria

From September 2017 we will prospectively enroll all adult patients with a GCS 9-15 that seek the ED within 24h after TBI.

Exclusion criteria

We will exclude:

- patients younger than 18 years of age;
- patients without a Swedish personal identification number due to difficulties in performing the follow up phase;

- all patients that refuse to participate.

Primary endpoint

The primary endpoint for this study will be the sensitivity, specificity, predictive values and likelihood ratios for the SNC13 for identifying traumatic intracranial complications.

Definition

Traumatic intracranial complications are defined as a composite variable of death as consequence of the TBI, need for neurosurgical intervention or marked abnormality on CT. CT abnormalities are defined as any new, acute, traumatic intracranial pathology including intracranial hematomas of any size, cerebral contusions and depressed skull fractures.

Secondary endpoints

- Measure the sensitivity, specificity, predictive values and likelihood ratios for the SNC13 for identifying patients needing neurosurgery or neurointensive care for the TBI within the first week following trauma.
- Measure the sensitivity, specificity, predictive values and likelihood ratios for the SNC13 for identifying patients with new, acute, traumatic intracranial pathology on CT including intracranial hematomas of any size, cerebral contusions and depressed skull fractures.
- Measure the sensitivity, specificity, predictive values and likelihood ratios for the SNC13 for identifying patients with clinically relevant CT findings (according to the CCHR)¹², defined as contusions larger than 5mm in diameter, subarachnoid bleeding thicker than 1mm, subdural hematoma thicker than 4mm, pneumocephaly that will need intervention, depressed skull fracture through the inner table.
- We will calculate sensitivity, specificity, predictive values and likelihood ratios of each guideline in identifying traumatic intracranial CT finding when applied to the same TBI population. We will also measure frequency of CT scans. We will investigate the performance of the SNC13 in comparison to other guidelines in reducing CT frequency without missing complications. We hypothesize that the implementation of a biomarker as S100B into clinical guidelines will achieve a further reduction in CT scans. Accuracy variables will be statistically compared with Chi-squared test.
- Measure performances of novel biomarkers such as GFAP, SBP-50 and TAU. S100B is the most studied brain biomarker and is the only one that is clinically used as a screening tool. However, S100B is not the perfect brain biomarker for TBI and new

biomarkers appear promising. In a explorative analysis we will compare S100B with GFAP, SBP-50 and TAU on the same selected mTBI population in order to determine the potential value of a panel of biomarkers for identifying high and low risk patients. We will calculate sensitivity, specificity, predictive values and likelihood ratios of each biomarker in identifying traumatic intracranial CT finding when applied to the same TBI population. ROC curves will be calculated in order to compare cut off values. We will also use the net reclassification index to see if each biomarker improves the accuracy of the classification.

- The final aspect that we would like to study is the derivation of a new improved guideline: binary logistic regressions analysis of all the variables taken into account and registered during the study will be performed. We will a priori divide the population into a derivation cohort, obtain ROC curves, and use these cutoffs after the bootstrapping process and other clinical and biochemical variables to construct a mode losing multivariable analysis.

Guidelines

A secondary goal of the study is to compare how the same mTBI population would be managed according to 7 guidelines that are clinically used in this particular patient group; we included the Canadian CT Head Rule¹³ (CCHR), the New Orleans criteria¹⁴ (NOC), the National Institute of Clinical Excellence¹⁵ (NICE), the CT in head injury patients Prediction Rule¹⁶ (CHIP) , the Neurotraumatology Committee of the World Federation of Neurosurgical Society¹⁷ (NCWFNS), the National Emergency X-Radiography Utilization Study II¹⁸ (NEXUS-II) and the SNC 2013¹⁹.

Each guideline has specific inclusion and exclusion criteria, and outcome measures, see table 2.

For each guideline patients will be divided into different groups: those who should be dismissed without a CT, those who should do a CT and those who do not fit the inclusion criteria for the guideline. A comparison of the 7 guidelines is shown in table 3.

The CCHR includes only patients with GCS 13-15 that have suffered LOC, have amnesia for trauma or are disoriented. Patients are divided into a high risk group, where CT is mandatory because of elevated risk for neurosurgical intervention, and medium risk for CT complications, in which case CT is only recommended. Both groups are analyzed independently but reported together for the group where CT scan should be performed. The CCHR primary outcome measure is the need for neurological intervention and the secondary

outcome is clinically relevant brain injury on CT. Clinically relevant CT findings are defined as contusions larger than 5mm in diameter, subarachnoid bleeding thicker than 1mm, subdural hematoma thicker than 4mm, pneumocephaly that will need intervention, depressed skull fracture through the inner table.

The NOC includes only patients with GCS of 15, thus according to these guidelines patients with GCS 14 or less were considered to have an indication for CT²⁰. The NOC outcome measure is any acute traumatic intracranial lesion on CT.

The NICE guidelines stratify patients that are eligible for CT into two groups, those who should undergo a CT within 1 hour and those within 8 hours. Both groups are analyzed independently but reported together for the group where CT scan should be performed.

The CHIP prediction rule does not have strict inclusion criteria, and recommends CT in the presence of one major or at least 2 minor risk factors. Both groups are analyzed independently but reported together for the group where CT scan should be performed. The CHIP primary outcome measure is any intracranial traumatic finding on CT, secondary outcome is all neurosurgical intervention after the initial CT.

The NCWFNS guidelines identify three levels of risk for intracranial complications. Low risk patients can be dismissed without any further investigation while patients with medium and high risk should have a CT scan and therefore are analyzed together.

NEXUS II does not stratify patients or take into account injury mechanism, it focuses mostly on symptoms at presentation at ED. The NEXUS II outcome measure is any intracranial injury on CT.

The second important aim was to compare the SNC13 to the other 6 guidelines. Different guidelines applied to the same population will perform with very different results, as previous studies have already shown^{23, 24}. The first aspect to be discussed in this comparative work is how many patients of this TBI population could be managed according to different guidelines. Both NOC, NICE and CCRH guidelines have strict inclusion criteria that may exclude a substantial portion of the TBI patients leaving physicians with no other choice than CT. Nevertheless, more flexible guidelines with no exclusion criteria like CHIP prediction rule or the NCWFNS guidelines have been proven to only marginally reduce the number of CTs. Nevertheless, beside restricted inclusion criteria, the NICE guidelines have shown to be one of the better performing guidelines for reducing CT frequency²³.

In the SNC13 guidelines, all patients could be managed with no exclusion criteria pre-defined, except for the time frame of 24h. According to previous studies, we would have expected a S100B negative rate for about 30% of sampled patients but, considering the new grading of patients, we expect better performances.

S100B is not the perfect biomarker for mTBI considering its low specificity. The perfect biomarker should be able to be brain specific, easily detectable, have a high sensitivity for intracranial complications and adverse outcome, with 100% negative predictive value and high clinical specificity. In recent years researchers agree on the possibility of defining a brain biomarker-panel; it therefore is fundamental to compare a well-studied biomarker as S100B with other new biomarkers. . The present study includes the most promising of these.

Strength and limitations

The main strength of this study is its design being an adequately powered multicenter study. Another important aspect is that it tests the SCN13 in the health care system for which it was intended for.

However every study has its limitation: a proper validation should be performed with a randomized study design; however this method would be ethically questionable.

The SNC13 were designed primarily for the Scandinavian health care system and its validity outside Scandinavia cannot be assumed.

Biomarker analysis will only be performed in a pre-defined subgroup of patients. This could lead to selection bias; however, the remaining patients do not have any theoretical advantage in management with biomarker results.

Variable	Data Format
Demographic/anamnestic variables	
Age	Years (continuous)
Gender	Male/female
Cause of injury	Patient report
Pedestrian/cyclist versus vehicle	Yes/no
Ejected from vehicle	Yes/no
Fall	Yes/no
Fall >1m	Yes/no
Signs of skull fracture	Yes/no
Contusion of the skull	Yes/no
Fracture above clavicles	Yes/no
Alcohol/drug intoxication	Yes/no
Ethanol levels	mmol/l (continuous)
LOC*	Yes/no
Duration LOC	Minutes (continuous)
Amnesia	Yes/no
Duration Amnesia	Minutes (continuous)
Persistent anterograd amnesia	Yes/no
Headache	Yes/no
Worsening headache	Yes/no
Vomiting episodes	Number (continuous)
Neurological deficit	Yes/no
Pretraumatic seizure	Yes/no
Posttraumatic seizure	Yes/no
GCS	Number (continuous)
GCS deterioration**	Number (continuous)
Antiplatelet medication	Yes/no
Anticoagulation therapy	Yes/no
Drug registration	Drug name
Bleeding disorder	Yes/no
Shunt-treatment	Yes/no
Dismissed***	Yes/no
S100B	µg/L (continuous)
CT	Yes/no
Admitted	Yes/no
Other causes to admission than TBI	Yes/no
Length of admission	Days (continuous)
Complications during admission	Yes/no

* LOC= loss of consciousness

** deterioration of GCS 2 after injury

*** dismissed with no intervention (CT or admission)

Table 1. variables studied

[figure not shown]
	CCHR	NOC	NICE	CHIP	NCWFNS	NEXUS II	SNC13
Inclusion criteria	Age ≥ 16 Presenting within 24h of head injury	Age ≥ 18 Presenting within 24h of head injury GCS 15	Age ≥ 18	Age ≥ 16 Presenting within 24h of head injury GCS 13-14 or GCS 15 and LOC or amnesia or pst-traumatic seizure or vomiting or severe headache or alcohol/drug intoxication or coagulopathy/ oral anticoagulants or injury above the clavicle or neurological deficit	Age ≥ 18 Presenting within 12h of head injury GCS 14-15	Age ≥ 18 GCS 15	Age ≥ 18 Presenting within 24h of head injury GCS 9-15
Exclusion criteria	-No clear history of trauma as primary event -Penetrating skull injury or depressed fracture -bleeding disorder or oral anticoagulants - neurological deficit	GCS ≤14					
Primary outcomes	Any need for neurological intervention	Acute traumatic intracranial lesion on CT		Any intracranial traumatic finding on CT		Any intracranial injury on CT	Any neurosurgical intervention
Secondary outcomes	Clinically relevant brain injury on CT			All neurosurgical intervention after initial CT			Any non-neurosurgical intracranial traumatic complications

Table 2. inclusion criteria, exclusion criteria, primary outcomes, secondary outcomes

Clinical findings	CCHR	NOC	NICE	CHIP	NCWFNS	NEXUS II	SNC 2013
Age	≥65	>60	≥65	≥60 major 40-60 minor	>60	≥65	≥65 and anti-platelet treatment
Pedestrian/cyclist versus vehicle	Minor		Minor	Major			
Ejected from vehicle	Minor		Minor	Major			
Fall >1m	Minor		Minor	Minor			
Signs of skull fracture	Any	Any	Any	Any	Any	Any	Any
Contusion of the skull						Any	
Fracture above clavicles		Any					
Alcohol/drug intoxication	Any				Any		
LOC*	Inclusion	Inclusion	Inclusion	Minor	Any		Low risk
Amnesia	Retrograde > 30 min	Antegrade	Retrograde > 30 min	≥4h major 2-<4h minor	Any	-	-
Headache		Severe			Any		
Vomiting episodes	>2	Any	>2	Major	Any	>2	>2 and GCS 14 low-risk
Neurological deficit	Excluded	Excluded	Any	Minor	Any	Any	Any
Pretraumatic seizure					Yes		
Posttraumatic seizure	Excluded	Any	Any	major	Any		Any
GCS <15	After 2h	Exclusion	After 2h	≥2 points deterioration Major 1point=minor	Always	Always	14 and no other risk-factor= low risk
Antiplatelet medication							And ≥65y
Anticoagulation therapy	Exclusion	-	Any	Major	Any	Any	Any
Bleeding disorder	Exclusion			Major			Any
Shunt-treatment					Any previous neurosurgical intervention		Yes

Table 3. Comparison of the 7 guidelines used in clinical practice for initial screening of TBI.

Figure 1: Algorythm for eligibility

REFERENCES

¹ Cassidy JD, Carroll LJ, Peloso PM, Borg J, von Holst H, Holm L, Kraus J, Coronado VG; WHO Collaborating Centre Task Force on Mild Traumatic Brain Injury. Incidence, risk factors and prevention of mild traumatic brain injury: results of the WHO Collaborating Centre Task Force on Mild Traumatic Brain Injury. *J Rehabil Med.* 2004 Feb;(43 Suppl):28-60.

² Peeters W, van den Brande R, Polinder S, Brazinova A, Steyerberg EW, Lingsma HF, Maas AI. Epidemiology of traumatic brain injury in Europe. *Acta Neurochir (Wien).* 2015 Oct;157(10):1683-96

³ McKinlay A, Grace RC, Horwood LJ, Fergusson DM, Ridder EM, MacFarlane MR. Prevalence of traumatic brain injury among children, adolescents and young adults: prospective evidence from a birth cohort. *Brain Inj.* 2008 Feb;22(2):175-81

⁴ Servadei F, Teasdale G, Merry G; Neurotraumatology Committee of the World Federation of Neurosurgical Societies. Defining acute mild head injury in adults: a proposal based on prognostic factors, diagnosis, and management. *J Neurotrauma.* 2001 Jul;18(7):657-64.

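### Table 1 is said to hold every predictor for the seven guidelines, but it cannot supply one NCWFNS criterion (previous neurosurgery other than a shunt) or one CHIP entry criterion (any injury above the clavicle)

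*Protocol*

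**What the plan says.** The Design section of the protocol promises: "All data necessary for analysis including predictor variables and outcome data for all the seven guidelines included in the study will be registered", and cites Table 1 as the list.

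**NCWFNS.** In the shunt row of Table 3 the NCWFNS entry is "Any previous neurosurgical intervention", while the SNC13 entry in the same row is a plain yes. Table 1 has one yes/no item for shunt treatment and no other item on neurosurgical history. The Guidelines section says that NCWFNS medium-risk and high-risk patients should have CT and low-risk patients can go home without further investigation.

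**CHIP.** Table 2 admits patients with GCS 13-14, or with GCS 15 plus at least one of a list of alternatives that ends with "injury above the clavicle or neurological deficit". The nearest items in Table 1 are "Signs of skull fracture", "Contusion of the skull" and "Fracture above clavicles". The Guidelines section, however, states: "The CHIP prediction rule does not have strict inclusion criteria".

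**Use.** Under Guidelines, each patient is sorted for each guideline into those who can be dismissed without CT, "those who should do a CT and those who do not fit the inclusion criteria for the guideline". The secondary endpoints then compare accuracy and CT frequency across guidelines.

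**The concern.** A guideline can be scored only on what was recorded. Where the recorded item is narrower than the criterion, patients who meet the criterion are coded as not meeting it. The two gaps act at different points:

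- For NCWFNS the missing item drives the CT decision. The error moves patients from CT to no CT, which understates NCWFNS CT frequency and can produce a missed complication that the guideline itself would not have missed.
- For CHIP the missing item governs entry. The error moves patients out of the guideline altogether.

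SNC13's own shunt criterion is recorded exactly as Table 3 states it, so the narrowing in that row falls on the comparator and not on the guideline under validation. The Discussion names the number of patients each guideline can manage as the first thing to be examined in the comparison, and eligibility errors bear directly on that. An analysis plan cannot supply a variable that was not collected.

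**Working it through.** The plan states no figure on this point, so the check matches the tables and then sizes the effect under stated assumptions.

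**1. NCWFNS, Table 3 against Table 1**
- Needed: any earlier neurosurgery. Recorded: shunt treatment, yes/no.
- Not captured: earlier neurosurgery without a shunt.
- Who is misclassified: only patients with no other NCWFNS trigger. Table 3 gives many others, including age over 60, LOC, amnesia, headache, vomiting, intoxication, GCS below 15, seizure, deficit and anticoagulation.

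Inputs from the Sample size section: 2490 patients and 5% prevalence of the primary outcome.
- Expected events: 2490 × 0.05 = 124.5, about 125.
- Cost of one event wrongly scored as no CT: 1/125 = 0.8 percentage points of sensitivity.
- Assumed share with non-shunt neurosurgery as the sole trigger (not in the protocol), 0.2% to 2%: 2490 × 0.002 = 5 and 2490 × 0.02 = 50 patients. NCWFNS CT frequency would be understated by 0.2 to 2 points.
- If those patients had the cohort's 5% prevalence: 5 × 0.05 = 0.25 and 50 × 0.05 = 2.5 expected events.

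The 0.8 points uses all events in the cohort. Table 2 restricts NCWFNS to GCS 14-15 within 12 hours, and the guideline comparison uses CT findings, which are one component of the primary composite. Either restriction gives fewer events, so each one would weigh more.

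**2. CHIP, Table 2 against Table 1**
- Needed: any injury above the clavicle. Recorded: skull-fracture signs, skull contusion, fracture above the clavicles.
- Not captured: other injuries, such as a facial or neck wound.
- Who is affected: GCS 15 patients with none of the other alternatives in Table 2.
- Example: a 70-year-old with GCS 15, a facial laceration and no other entry feature. Age 60 or over is a CHIP major factor in Table 3 but not an entry criterion in Table 2. Applied literally, this patient should be in the CT group but is coded as not fitting the guideline.
- Assumed share of 1% to 10% (not in the protocol): 2490 × 0.01 = 25 and 2490 × 0.10 = 249 patients misplaced.

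**3. Direction of the CHIP error**

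Assume for illustration that all 2490 should be eligible, 249 are misplaced and half of those (124.5) carry a CHIP CT indication. This leaves 2490 − 249 = 2241 coded eligible.

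| CHIP CT rate if fully recorded | Rate among those coded eligible | Rate over all 2490, misplaced counted as no CT | Rate over all 2490, misplaced counted as CT |
|---|---|---|---|
| 50% (1245) | (1245 − 124.5)/2241 = 50.0% | 1120.5/2490 = 45.0% | (1120.5 + 249)/2490 = 55.0% |
| 70% (1743) | (1743 − 124.5)/2241 = 72.2% | 1618.5/2490 = 65.0% | (1618.5 + 249)/2490 = 75.0% |

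The same recording gap can leave the rate unchanged, lower it or raise it, depending on the denominator and on how patients outside the guideline are counted.

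**The case against.** The strongest reply concerns CHIP. The Guidelines section says CHIP has no strict inclusion criteria, and the Discussion groups it with flexible guidelines that have no exclusion criteria. Applied that way, nobody is lost through this item. One could also argue that every enrolled patient has a head injury and so meets the criterion automatically. In Table 3 the CHIP cell for fracture above the clavicles is blank, so the item affects CHIP entry and not its CT recommendation. This stands in part: the CHIP gap arises only if Table 2 is applied as written, and the protocol does not say which description governs. That conflict itself needs resolving.

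On NCWFNS, the many other triggers mean that few patients would depend on this item alone. That also stands, and it limits the size of the error but does not remove it.

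Four stronger readings are tempting, and the protocol does not support them:
- **That Table 1 captures only fractures above the clavicle.** It also has skull contusion and skull-fracture signs.
- **That everyone with non-shunt neurosurgery is misclassified.** Only those with no other trigger are.
- **That CHIP's CT count is necessarily too low.** The direction is not fixed, as the table above shows.
- **That the loss cannot be repaired after enrolment.** The follow-up section describes nationwide access to medical records, so earlier neurosurgery could often be recovered. However, the protocol plans record review only for patients who cannot be reached, and only for complications or death. Minor soft-tissue findings are harder to recover.

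Finally, the case-report form is not shown. It is described under general headings that include history and examination, so it may be wider than Table 1. The protocol names neither item.

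**Conclusion.** The point holds as a gap between the promise in the Design section and Table 1. The NCWFNS half is a direct mismatch on a criterion that decides CT. Followed as written, the plan scores sole-criterion patients as no CT, understates NCWFNS CT frequency and may create a miss worth about 0.8 points of sensitivity per event, given 2490 patients and 5% prevalence. The number affected is not stated and is probably small; the 5 to 50 patients shown rest on an assumed share.

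The CHIP half holds only if Table 2 is applied literally. Its size is unknown (25 to 249 patients on an assumed 1% to 10%), and its effect on the CT rate has no fixed direction.

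A reader might infer that the validation of SNC13 is compromised. It is not: the primary endpoint concerns SNC13 alone, and its shunt item is recorded. Only the secondary comparison of guidelines is touched.

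**What to change.** - Add two yes/no rows to Table 1 and the case-report form: any previous neurosurgery, and any injury above the clavicles. Keep the existing shunt, skull contusion, skull-fracture and fracture rows.
- Score the NCWFNS criterion from the first new row and CHIP eligibility from the second.
- Reconcile the statement on CHIP inclusion in the Guidelines section with the CHIP list in Table 2, and state which one is applied in the analysis.
- If the items cannot be collected, recover previous neurosurgery from medical records where possible, name the proxy used for each criterion, and report NCWFNS and CHIP results under both extreme codings (all unknown patients positive, all negative).

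Before enrolment the cost is two tick boxes and a sentence of text, with no extra procedure for patients. The protocol is dated 30 August 2017 and enrolment is to start in September 2017, so the change is cheapest at once. For patients already enrolled, the cost is a record check for neurosurgical history and the two sensitivity codings.

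### Table 1 records neither retrograde amnesia nor headache severity, so the CCHR, NICE and NOC criteria and one route into CHIP cannot be scored as the protocol defines them

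*Protocol*

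**What the plan says.** Methods, Design: "All data necessary for analysis including predictor variables and outcome data for all the seven guidelines included in the study will be registered", and the sentence points the reader to Table 1.

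Table 3, amnesia row: CCHR and NICE each have "Retrograde > 30 min". NOC asks for anterograde amnesia, CHIP for duration alone ("≥4h major 2-<4h minor"), and NCWFNS for any amnesia. SNC13 has a dash.

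Table 3, headache row: NOC requires severe headache and NCWFNS any headache. The other columns, including SNC13, are blank.

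Table 2 lists "severe headache" among the alternative routes into CHIP for a patient with GCS 15.

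Table 1 records amnesia as yes/no, "Duration Amnesia" in minutes, and "Persistent anterograd amnesia" as yes/no. It records headache as yes/no and "Worsening headache" as yes/no.

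The Guidelines section sorts patients under each guideline into discharge without CT, CT, or outside that guideline's inclusion criteria. It gives no rule for turning Table 1 variables into the Table 3 criteria.

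**The concern.** Two of the listed comparator criteria need information that Table 1 does not hold: whether amnesia was retrograde and for how long, and how severe the headache was. This is a matter of data capture. A later analysis plan can choose a proxy, but it cannot recover a retrograde duration or a severity grade that was never recorded in the emergency department.

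The secondary comparison is at stake. The protocol will compare SNC13 with the other guidelines on CT frequency and missed complications, and it hypothesises that a biomarker-based guideline will reduce CT further. SNC13 uses neither item, so any scoring error moves comparators and leaves SNC13 where it is. NICE is among those affected, and the Discussion names it as one of the better performers on CT frequency.

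**Working it through.** No stated figure is in dispute. The check sets the criteria against the recorded variables and then asks which way the error can go.

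**Step 1: can each criterion be scored from Table 1?**

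| Guideline and item | Needs | Table 1 offers | Scorable as defined? |
|---|---|---|---|
| CCHR, NICE amnesia | retrograde type and duration over 30 min | one untyped duration | No |
| NOC amnesia | anterograde type | persistent anterograde, yes/no | Approximately |
| CHIP amnesia | duration only | untyped duration | Yes |
| NCWFNS amnesia | any | yes/no | Yes |
| NOC headache | severe | yes/no; worsening yes/no | No |
| NCWFNS headache | any | yes/no | Yes |
| CHIP entry, headache route | severe | yes/no; worsening yes/no | No |
| SNC13 | neither item | not needed | Not affected |

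No guideline in Table 3 uses worsening headache.

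**Step 2: two patients, one record.** Patient A has 45 minutes of resolved post-traumatic amnesia and no retrograde amnesia. Patient B has 45 minutes of retrograde amnesia only. Both are recorded as amnesia yes, 45 min, persistent anterograde no. B meets the CCHR and NICE criterion and A does not, and no rule applied to these Table 1 fields can separate them. The same holds for a mild and a severe headache, neither of them worsening: both are recorded as headache yes, worsening no.

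**Step 3: direction for CCHR and NICE.** Let q be the share of patients with no other CT criterion under the guideline, a the share with recorded amnesia over 30 min, and r the share of those in whom it is truly retrograde over 30 min. Treat q and a as independent.

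- Any amnesia over 30 min counted: shift in CT frequency = +q·a·(1 − r)
- Criterion left unscored: shift = −q·a·r

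The protocol gives none of these rates. Assume q 0.3 to 0.7, a 0.02 to 0.10, r 0.2 to 0.8:

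- Broad: from 0.3 × 0.02 × 0.2 = +0.12 points to 0.7 × 0.10 × 0.8 = +5.6 points
- Unscored: from −(0.3 × 0.02 × 0.2) = −0.12 points to −(0.7 × 0.10 × 0.8) = −5.6 points

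**Step 4: direction for NOC headache.** Let h be the share with any headache, s the severe share of those, and w the worsening share of those.

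- Any headache counted: +q·h·(1 − s)
- Worsening headache counted instead of severe: q·h·(w − s)

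Assume q 0.1 to 0.5, h 0.3 to 0.5, s 0.1 to 0.3, w 0.03 to 0.10:

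- Any headache: from 0.1 × 0.3 × 0.7 = +2.1 points to 0.5 × 0.5 × 0.9 = +22.5 points
- Worsening only: from 0 (where w = s = 0.10) to 0.5 × 0.5 × (0.03 − 0.30) = −6.8 points

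These figures show only that the sign changes with the scoring rule. They rest on assumed rates and do not estimate the effect in this study.

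**Step 5: accuracy measures.** Relative to correct scoring, a broad proxy that captures every true case can only add positives. Comparator sensitivity then stays or rises, and specificity stays or falls. Counting the criterion as not met removes positives, so sensitivity stays or falls and specificity stays or rises.

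**The case against.** A reader might infer that the gap inflates comparator CT frequency and so flatters SNC13. The document does not support this. It never says that the untyped duration or the plain headache item will stand in for the listed criteria. If a criterion goes unscored, or worsening headache replaces severe headache, comparator CT frequency can fall. Even under broad scoring, the added positives can raise comparator sensitivity, which works against SNC13 on missed complications. The bias therefore cannot be called one-directional.

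Nor can the size be stated. Saying that 5% of patients mis-scored gives 5 percentage points only restates the assumption. Applying it to all 2490 patients also ignores those outside each guideline's inclusion criteria.

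Three further limits are fair. Some amnesia items can be scored, exactly or approximately (NOC, CHIP, NCWFNS). Severe headache is only one of many routes into CHIP, so exposure there is probably small. The case-report form is not shown and may hold more than Table 1; scoring details are also commonly left to an analysis plan.

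All of this narrows the point without removing it. The Design section offers Table 1 as the complete list, and on that list three comparators and one entry route cannot be scored as defined.

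**Conclusion.** The point holds as an internal inconsistency between the Design section's claim of completeness and Tables 1, 2 and 3. As written, the study cannot apply the CCHR and NICE amnesia criterion, the NOC headache criterion, or the severe-headache route into CHIP. The resulting misclassification affects comparators only and is confined to the secondary comparison of CT frequency, sensitivity and specificity. The accuracy of SNC13 itself, the primary endpoint, is untouched.

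Neither direction nor size is fixed by the protocol: direction turns on an unstated scoring rule, and size on rates that are not given. The conclusion assumes that Table 1 is the full list of recorded predictors, as the Design section says. It should be corrected, because data not captured at presentation cannot be restored by analysis and the correction is cheap.

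**What to change.** In Table 1 and the case-report form, replace the untyped amnesia duration with two items, retrograde and anterograde/post-traumatic, each in minutes. Record headache as none, not severe or severe. Score CCHR, NICE, NOC and CHIP eligibility from these items.

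For patients already registered without them, report each affected comparator's CT frequency, sensitivity and specificity under two bounds:

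- the broad proxy counted as meeting the criterion (any amnesia over 30 min; any headache);
- the criterion counted as not met.

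The amnesia bound is a true upper bound only if the recorded duration is at least as long as the retrograde part. State how staff were told to fill that field.

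The cost is a slightly longer triage form and one extra scoring run. If the form already holds these items, it is enough to align Table 1 with it and state the scoring rule.
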